Appendix 12 Category of Adverse Events of Special Interest

List number	Category of adverse events of special interest
01	Falls and injuries
02	Drug reaction with eosinophilia and systemic systems
03	Disorientation and confusion
04	Driving and road traffic accident
05	Abuse liability
06	Abnormal liver adverse events
07	Somnolence and sedation
08	Fatigue and lethargy
09	Suicidal ideation and behavior
10	Significant cardiovascular disease
11	Cognitive function
12	Depression and depressed mood
13	Psychiatric disorders
14	Seizures

Appendix 13 Modify registry of severe cutaneous adverse reaction criteria for Drug reaction with eosinophilia and systemic systems (DRESS)

Only patients meeting the criteria will be presented.

At least 3 of the following criteria should be present for hypersensitivity syndrome or DRESS:

- 1. Acute skin rash
- 2. Involvement of at least 1 internal organ
- 3. Enlarged lymph nodes of at least 2 sites
- 4. One of the following blood count abnormalities (limits provided by laboratory):
 - lymphocytes above or below the laboratory limits
 - eosinophils above the laboratory limits (in % or absolute count)
 - platelets below the laboratory limits
- 5. Fever above 38 degrees Celsius

The adverse events should occur within 30 days of each other (There should be temporal proximity for the onset of these AEs.). Some PTs may be mentioned in more than one SOC. (within 1 month of each other).

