Appendix 13.2 Involvement of at least 1 internal organ

Blood and lymphatic system disorders SOC	Cardiac disorders SOC:	Endocrine disorders SOC:
Agranulocytosis Aplastic anemia Aplasia pure red cell Autoimmune lymphoproliferative syndrome Autoimmune neutropenia Autoimmune pancytopenia Blood disorder Bone marrow disorder Bone marrow failure Bone marrow toxicity Coagulopathy Disseminated intravascular coagulation Disseminated intravascular coagulation in newborn Drug reaction with eosinophilia and systemic symptoms Eosinophilia Febrile neutropenia Granulocytopenia Haemolytic anemia Hemolysis Hypereosinophilic syndrome Leukemoid reaction Leukopenia Lymphocytosis Lymphopenia Hypersensitivity vasculitis Lymphadenitis Lymphadenopathy Lymphoma Monocytosis Mononucleosis Neutropenia Pancytopenia Platelet disorder Platelet toxicity Splenitis Splenomegaly Splenosis Thrombocytopenia	Autoimmune myocarditis Cardiomyopathy Endocarditis Eosinophilic myocarditis Myocarditis Pericarditis Pericardial effusion Pericardial disease Pleuropericarditis	Adrenalitis Autoimmune thyroiditis Thyroiditis

Eye disorders SOC	Gastrointestinal disorders SOC	Hepatobiliary disorders SOC
Eye allergy	Allergic colitis	Autoimmune hepatitis
Eye swelling	Colitis	Amylase increased
Iritis	Eosinophilic colitis	Blood trypsin increased
Iridocyclitis	Eosinophilic oesophagitis	Cholangitis
Optic neuritis	Gastritis	Cholecystitis
Retinitis	Gingival edema	Hepatic failure
Uveitis	Gingival swelling	Hepatic functional abnormal
Vitritis	Gingivitis	Hepatic encephalopathy
Scleritis	Glossitis	Hepatic infiltration eosinophilic
	Enteritis	Hepatitis
	Mouth ulceration	Hepatitis acute
	Mesenteritis	Hepatitis toxic
	Edema mouth	Hepatocellular injury
	Oropharyngeal swelling	Hepatomegaly
	Parotitis	Hepatosplenomegaly
	Pancreatitis	Hepatorenal failure
	Periodontitis	Hepatorenal syndrome
	Sialadenitis	Hepatotoxicity
	Stomatitis	Hyperbilirubinemia
	Swollen tongue	Hyperbilirubinemia neonatal
	Tongue oedema	Hyperlipidemia
	Vasculitis gastrointestinal	Jaundice
		Jaundice neonatal
		Liver disorder
		Lipase abnormal
		Lipase increased
		Edema due to hepatic disease
		Edematous pancreatitis
		Pancreatic enzymes increased
		Pancreatic hemorrhage
		Pancreatic necrosis
		Pancreatitis (any PT that includes the word "pancreatitis")
		Pancreatorenal syndrome
		Peripancreatic fluid collection
		Swollen tongue

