General disorders and administration site conditions SOC:	Immune system disorders SOC (Part 1)	Immune system disorders SOC (Part 2)
Influenza like illness	Allergic bronchitis	Eyelid edema
Malaise	Allergic cough	Eosinophilic fasciitis
Multi-organ failure	Allergic cystitis	Face edema
Neonatal multi-organ failure	Allergic keratitis	Hypersensitivity
	Allergic oedema	Immune thrombocytopenic purpura
	Allergic sinusitis	Glomerulonephritis
	Alveolitis allergic	Laryngeal edema
	Anaphylactic reaction	Lip edema
	Anaphylactic shock	Lip swelling
	Anaphylactoid reaction	Myasthenia Gravis
	Anaphylactoid shock	Myositis
	Asthma	Nephrogenic systemic fibrosis
	Angioedema	Edema mouth
	Antiphospholipid syndrome	Panniculitis
	Autoimmune disorder	Pemphigus
	Autoimmune hepatitis	Pemphigoid
	Biliary cirrhosis primary	Periorbital edema
	Biliary cirrhosis	Pruritus allergic
	Bronchospasm	Polymyositis
	Circumoral edema	Reaction to drug excipients
	Cholangitis sclerosing	Sarcoidosis
	Dermatomyositis	Serum sickness
	Drug hypersensitivity	Systemic lupus erythematosus
	Drug reaction with eosinophilia and systemic symptoms	Systemic sclerosis
	Encephalitis	Type IV hypersensitivity reaction
	Encephalopathy allergic	Vitiligo

Investigations SOC: Hematologic	Investigations SOC: Immunologic	Investigations SOC: others
Any PT that reflects increased, decreased or abnormal MedDRA Hematology investigations (incl blood groups) HLGT Any PT that reflects increase or abnormal under MedDRA Hepatobiliary investigations HLGT	Any PT that reflects a positive or abnormal result under MedDRA Immunology and allergy investigations HLGT, and Investigations, imaging and histopathology procedures NEC, HLGT	Alanine aminotransferase Amylase Aspartate aminotransferase Bilirubin conjugated Blood amylase Blood bilirubin Blood bilirubin unconjugated Gamma-glutamyltransferase increased Lipase Liver function test Transaminases Biopsy liver abnormal Lung Biopsy lung abnormal Renal Blood creatinine increased Blood creatinine abnormal Blood urea increased Blood urea abnormal Creatinine renal clearance decreased Glomerular filtration rate decreased Blood urine Cells in urine Eosinophils urine Protein urine Red blood cells urine Urinary casts Urinary casts present Biopsy kidney abnormal Skin Biopsy skin abnormal

Musculoskeletal and connective tissue disorders SOC:	Neoplasms benign, malignant and unspecified (including cysts and polyps) SOC	Nervous system disorders SOC

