Appendix 13.3 Enlarged lymph nodes of at least 2 sites

Search for PT including the word “Lymphadenopathy” alone or as part of another PT

Such as some examples are given below:

- Lymphadenopathy Mediastinal
- Paratracheal Generalized
- Retroperitoneal
- Vaccination site

Search for other PT that could reflect lymphadenopathy

- Benign lymph node neoplasm
- Lymph node palpable
- Lymph node scan abnormal

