Appendix 13.4 One of the following blood count abnormalities

The search will use laboratory blood sample values along with their corresponding reference ranges

- Lymphocytes above or below lab limits
- Eosinophils above the lab limits
- Platelets below lab limits

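### The SAP's DRESS rule asks for 3 of 5 criteria but lets one finding count towards two, and its lymph-node search does not check the 2-site condition

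*SAP*

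**What the plan says.** SAP Section 12.7.2.3 summarises adverse events of special interest by treatment arm. DRESS is category 02 in Appendix 12, and Appendix 13 defines it: "At least 3 of the following criteria should be present for hypersensitivity syndrome or DRESS". The five criteria are (1) skin rash, (2) involvement of an internal organ, (3) enlarged lymph nodes, (4) a blood-count abnormality and (5) fever. The adverse events must fall within 30 days of each other.

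The sub-appendices say how each criterion is found:

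- **Criterion 2 (13.2).** A list of preferred terms. The blood and lymphatic column includes "Leukopenia Lymphocytosis Lymphopenia Hypersensitivity vasculitis Lymphadenitis Lymphadenopathy Lymphoma", and also eosinophilia, thrombocytopenia and febrile neutropenia. The investigations column adds "Any PT that reflects increased, decreased or abnormal MedDRA Hematology investigations".
- **Criterion 3 (13.3).** The criterion reads "Enlarged lymph nodes of at least 2 sites". The search takes the word lymphadenopathy "alone or as part of another PT". Its examples include a vaccination-site term, and a palpable lymph node also qualifies.
- **Criterion 4 (13.4).** Laboratory values are compared with reference ranges; the first entry is "Lymphocytes above or below lab limits". High eosinophils and low platelets also qualify.
- **Criterion 5 (13.5).** Pyrexia and similar terms, and every preferred term containing the word febrile.

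The only remark on repeated terms is that some appear under more than one system organ class. No sentence says that a term or finding may be used for one criterion only.

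**The concern.** A 3-of-5 rule is protective only if the criteria are met by different findings. Where one event scores twice, the effective threshold falls to two findings, and the reader of the table cannot tell from the count that this happened. Appendix 13 contains no medical confirmation step between the programmed rule and the table.

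DRESS is a serious diagnosis, so even one labelled case in a small crossover trial attracts attention. Two further features loosen the rule: the node search does not apply the condition in its own heading, and the blood-count criterion needs no change on treatment.

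**Working it through.** The plan states no figure on this point, so the check is a logic count. Each finding is mapped to the criteria whose list or search it satisfies, and the number of distinct criteria met is compared with 3.

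**Mappings, all from Appendix 13.**

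- Lymphadenopathy: criterion 2 (13.2 list) and criterion 3 (13.3 search; if 2 sites are enforced, only when 2 or more are recorded).
- Febrile neutropenia: criterion 2 (13.2 list) and criterion 5 (13.5, contains febrile).
- Lymphopenia, lymphocytosis, eosinophilia or thrombocytopenia as an adverse event: criterion 2. The matching laboratory value: criterion 4.
- Any lymphocyte value outside limits: criterion 4.
- Rash: criterion 1.

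**Criteria met out of 5.** The last column lets each finding score once and treats an adverse event and its own laboratory value as one finding.

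| Findings | As written, 13.3 search run literally | As written, 2 sites enforced | Each finding counted once |
|---|---|---|---|
| Lymphadenopathy at one site + out-of-range lymphocyte count | 3 (criteria 2, 3, 4) | 2 (2, 4) | 2 |
| Lymphadenopathy at 2 or more sites + the count | 3 (2, 3, 4) | 3 (2, 3, 4) | 2 |
| Febrile neutropenia + the count | 3 (2, 4, 5) | 3 (2, 4, 5) | 2 |
| Lymphopenia as an adverse event + its own count | 2 (2, 4) | 2 (2, 4) | 1 |
| The same + rash | 3 (1, 2, 4) | 3 (1, 2, 4) | 2 |

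Rows 2, 3 and 5 reach the threshold whichever way criterion 3 is read, so double counting stands apart from the site problem. Row 1 depends entirely on whether the 2-site condition is applied. Enforcing that condition alone repairs row 1 and leaves rows 2, 3 and 5 unchanged. Counting each finding once brings every row below 3.

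**Criterion 4.** SAP Section 12.7.3 schedules haematology at Screening and at D21 of each period. Appendix 13.4 asks for no toxicity grade and no change from Screening, so a patient out of range throughout meets it without any change on treatment. The 30-day window is worded for adverse events and their onset; it does not mention laboratory values.

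To show how easily this criterion could be met by chance, assume a probability p that a D21 lymphocyte value is out of range, and two independent D21 samples per patient. The documents give no such p, and repeated counts in one patient are in practice correlated, so this is only an illustration. The chance of at least one out-of-range value is 1 − (1 − p)²:

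- p = 0.025: 0.049, or 3.4 of 68 patients
- p = 0.05: 0.0975, or 6.6 of 68
- p = 0.10: 0.19, or 12.9 of 68

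These patients would still need the adverse-event part of the rule.

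**Size of one case.** With 68 patients per arm (the completer target in SAP Section 8.2; in a crossover each completer contributes to both arms), one case is 1/68 = 1.5 percentage points. With an assumed 70 exposed it is 1/70 = 1.4.

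**The case against.** The case for leaving the appendix alone has several parts.

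- **The 2-site condition is in the rule.** It appears in the criterion and in the heading of 13.3, and a search list finds candidates without cancelling the criterion. This stands against the one-site example. It does not answer the two-site or febrile neutropenia examples, and 13.3 still gives a programmer no way to establish sites.
- **A broad screen is meant to be sensitive.** Appendix 13 describes itself as a modified registry definition, and the source is not in the documents. Which terms count as organ involvement is a clinical choice. This stands: whether malaise, influenza-like illness or haematological terms belong in criterion 2 is for the sponsor's medical team. Letting one finding score twice is a separate matter, because it changes what a count of 3 means.
- **Other restrictions narrow the cases.** The adverse events must be within 30 days of each other and the tables count treatment-emergent events. The criterion 2 entry on abnormal haematology needs a coded adverse event, so a laboratory value alone does not meet it. All true, but none stops one adverse event scoring twice, and the SAP does not say whether the treatment-emergent condition reaches the laboratory value in criterion 4.
- **A wrong label would be visible.** Events are tabulated by preferred term and listed, and laboratory shifts are shown against baseline. That helps a careful reader trace a case but leaves the DRESS count as it is.

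**Conclusion.** The point holds as a defect in a safety case definition. Appendix 13 can tabulate as a 3-criterion DRESS case a patient with only two findings: lymphadenopathy (at 2 or more sites, or at one site if 13.3 is run literally) or febrile neutropenia, plus one out-of-range lymphocyte count. Criterion 3 and its search conflict, and criterion 4 accepts an abnormality already present at Screening.

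A reader might infer three stronger things that the documents do not support:

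- **That any single lymphadenopathy report plus a lymphocyte count is DRESS under the plan.** It is not if the 2-site wording is enforced.
- **That false cases are likely, for example through viral illness during the pandemic.** No event rate is given, and Protocol Section 12.6 requires symptoms to be replaced by the diagnosis once one is made, so separate malaise and fever records would mainly arise from undiagnosed illness.
- **That isolated cases would appear in the time-to-onset plots.** SAP Section 12.7.2.3 provides each plot only when more than 5 patients in each arm have an event, so the exposure is in the tables.

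The effect is confined to one descriptive category, at about 1.5 percentage points per misclassified case on the 68-patient assumption. No efficacy estimate, test or error rate changes. The correction should be made because it is cheap and changes the classification; ideally it is done before unblinding, since redefining a safety case afterwards is open to challenge.

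**What to change.** Make three changes to Appendix 13:

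1. State that each adverse event, together with its matching laboratory abnormality, counts towards only one criterion.
2. Reconcile 13.3 with the 2-site condition, by requiring two recorded sites or a term that denotes generalised lymphadenopathy.
3. Require the criterion 4 abnormality to be new or worse than Screening, and state how laboratory dates enter the 30-day window.

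The cost is appendix wording and minor programming. The screen becomes slightly less sensitive; patients who drop out of the DRESS count can still be listed for medical review. The content of the organ-involvement list need not change for this correction.

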Appendix 13.1 Acute skin reaction

Search in 'Skin and subcutaneous tissue disorders' SOC the following preferred term:

- Dermatitis (any Preferred Term that includes the word "dermatitis")
- Drug eruption
- Eczema
- Erythema multiforme
- Erythema nodosum

- Rash (any PT that includes the word “rash”)
- Skin lesion
- Skin reaction
- Skin exfoliation
- Stevens-Johnson Syndrome
- Toxic epidermal necrolysis
- Toxic skin eruption
- Urticaria

Appendix 13.2 Involvement of at least 1 internal organ

Blood and lymphatic system disorders SOC	Cardiac disorders SOC:	Endocrine disorders SOC:
Agranulocytosis Aplastic anemia Aplasia pure red cell Autoimmune lymphoproliferative syndrome Autoimmune neutropenia Autoimmune pancytopenia Blood disorder Bone marrow disorder Bone marrow failure Bone marrow toxicity Coagulopathy Disseminated intravascular coagulation Disseminated intravascular coagulation in newborn Drug reaction with eosinophilia and systemic symptoms Eosinophilia Febrile neutropenia Granulocytopenia Haemolytic anemia Hemolysis Hypereosinophilic syndrome Leukemoid reaction Leukopenia Lymphocytosis Lymphopenia Hypersensitivity vasculitis Lymphadenitis Lymphadenopathy Lymphoma Monocytosis Mononucleosis Neutropenia Pancytopenia Platelet disorder Platelet toxicity Splenitis Splenomegaly Splenosis Thrombocytopenia	Autoimmune myocarditis Cardiomyopathy Endocarditis Eosinophilic myocarditis Myocarditis Pericarditis Pericardial effusion Pericardial disease Pleuropericarditis	Adrenalitis Autoimmune thyroiditis Thyroiditis

Eye disorders SOC	Gastrointestinal disorders SOC	Hepatobiliary disorders SOC
Eye allergy	Allergic colitis	Autoimmune hepatitis
Eye swelling	Colitis	Amylase increased
Iritis	Eosinophilic colitis	Blood trypsin increased
Iridocyclitis	Eosinophilic oesophagitis	Cholangitis
Optic neuritis	Gastritis	Cholecystitis
Retinitis	Gingival edema	Hepatic failure
Uveitis	Gingival swelling	Hepatic functional abnormal
Vitritis	Gingivitis	Hepatic encephalopathy
Scleritis	Glossitis	Hepatic infiltration eosinophilic
	Enteritis	Hepatitis
	Mouth ulceration	Hepatitis acute
	Mesenteritis	Hepatitis toxic
	Edema mouth	Hepatocellular injury
	Oropharyngeal swelling	Hepatomegaly
	Parotitis	Hepatosplenomegaly
	Pancreatitis	Hepatorenal failure
	Periodontitis	Hepatorenal syndrome
	Sialadenitis	Hepatotoxicity
	Stomatitis	Hyperbilirubinemia
	Swollen tongue	Hyperbilirubinemia neonatal
	Tongue oedema	Hyperlipidemia
	Vasculitis gastrointestinal	Jaundice
		Jaundice neonatal
		Liver disorder
		Lipase abnormal
		Lipase increased
		Edema due to hepatic disease
		Edematous pancreatitis
		Pancreatic enzymes increased
		Pancreatic hemorrhage
		Pancreatic necrosis
		Pancreatitis (any PT that includes the word "pancreatitis")
		Pancreatorenal syndrome
		Peripancreatic fluid collection
		Swollen tongue

General disorders and administration site conditions SOC:	Immune system disorders SOC (Part 1)	Immune system disorders SOC (Part 2)
Influenza like illness	Allergic bronchitis	Eyelid edema
Malaise	Allergic cough	Eosinophilic fasciitis
Multi-organ failure	Allergic cystitis	Face edema
Neonatal multi-organ failure	Allergic keratitis	Hypersensitivity
	Allergic oedema	Immune thrombocytopenic purpura
	Allergic sinusitis	Glomerulonephritis
	Alveolitis allergic	Laryngeal edema
	Anaphylactic reaction	Lip edema
	Anaphylactic shock	Lip swelling
	Anaphylactoid reaction	Myasthenia Gravis
	Anaphylactoid shock	Myositis
	Asthma	Nephrogenic systemic fibrosis
	Angioedema	Edema mouth
	Antiphospholipid syndrome	Panniculitis
	Autoimmune disorder	Pemphigus
	Autoimmune hepatitis	Pemphigoid
	Biliary cirrhosis primary	Periorbital edema
	Biliary cirrhosis	Pruritus allergic
	Bronchospasm	Polymyositis
	Circumoral edema	Reaction to drug excipients
	Cholangitis sclerosing	Sarcoidosis
	Dermatomyositis	Serum sickness
	Drug hypersensitivity	Systemic lupus erythematosus
	Drug reaction with eosinophilia and systemic symptoms	Systemic sclerosis
	Encephalitis	Type IV hypersensitivity reaction
	Encephalopathy allergic	Vitiligo

Investigations SOC: Hematologic	Investigations SOC: Immunologic	Investigations SOC: others
Any PT that reflects increased, decreased or abnormal MedDRA Hematology investigations (incl blood groups) HLGT Any PT that reflects increase or abnormal under MedDRA Hepatobiliary investigations HLGT	Any PT that reflects a positive or abnormal result under MedDRA Immunology and allergy investigations HLGT, and Investigations, imaging and histopathology procedures NEC, HLGT	Alanine aminotransferase Amylase Aspartate aminotransferase Bilirubin conjugated Blood amylase Blood bilirubin Blood bilirubin unconjugated Gamma-glutamyltransferase increased Lipase Liver function test Transaminases Biopsy liver abnormal Lung Biopsy lung abnormal Renal Blood creatinine increased Blood creatinine abnormal Blood urea increased Blood urea abnormal Creatinine renal clearance decreased Glomerular filtration rate decreased Blood urine Cells in urine Eosinophils urine Protein urine Red blood cells urine Urinary casts Urinary casts present Biopsy kidney abnormal Skin Biopsy skin abnormal

Musculoskeletal and connective tissue disorders SOC:	Neoplasms benign, malignant and unspecified (including cysts and polyps) SOC	Nervous system disorders SOC
Arthralgia Arthritis Arthroplasty Ankle arthroplasty Hip arthroplasty Joint arthroplasty Knee arthroplasty Shoulder arthroplasty Joint swelling Joint warmth Lupus-like syndrome Myopathy Myositis Polyarthritis Tendonitis Tenosynovitis Synovitis Any PT under the MedDRA Connective tissue disorders (excl congenital) HLGT.	Lymphoma (any PT that includes the word "lymphoma") Pseudolymphoma	Acoustic neuritis Arachnoiditis CNS inflammation CNS ventriculitis Spinal cord infection Encephalitis (all PTs under Encephalitis NEC, HLT) Encephalopathy Leukoencephalopathy Leukoencephalomyelitis Meningitis (all PTs under Meningitis NEC, HLT) Myelitis Neuritis cranial Neuropathy peripheral Polyneuropathy Reye's syndrome Toxic optic neuropathy Vasculitis cerebral

Renal and urinary disorders SOC:	Respiratory, thoracic and mediastinal disorders SOC:	Vascular disorders SOC:
Anuria	Allergic bronchitis	Arteritis (any PT that includes the word "arteritis")
Cardiorenal syndrome	Acute interstitial pneumonitis	Capillaritis
Dialysis	Asthma	Vasculitis (any PT that includes the word "vasculitis")
Eosinophilic cystitis	Allergic granulomatous angiitis	
Hematuria	Alveolitis	
Hemodialysis	Alveolitis allergic	
Hemolytic uremic syndrome	Angiolympoid hyperplasia with Eosinophilia	
Hepatorenal failure	Eosinophilic bronchitis	
Hepatorenal syndrome	Eosinophilia myalgia syndrome	
Pancreatorenal syndrome	Eosinophilic pneumonia	
Peritoneal dialysis	Interstitial lung disease	
Edema due to renal disease	Pleural effusion	
Renal disorder	Pleurisy	
Renal failure	Pleurisy viral	
Renal impairment	Pleuropericarditis	
Nephropathy toxic	Pneumonitis	
Any PT under MedDRA	Pulmonary eosinophilia	
Nephropathies HLT	Pulmonary vasculitis	
	Pulmonary toxicity	

Renal and urinary disorders SOC:	Respiratory, thoracic and mediastinal disorders SOC:	Vascular disorders SOC:
Anuria Cardiorenal syndrome Dialysis Eosinophilic cystitis Hematuria Hemodialysis Hemolytic uremic syndrome Hepatorenal failure Hepatorenal syndrome Pancreatorenal syndrome Peritoneal dialysis Edema due to renal disease Renal disorder Renal failure Renal impairment Nephropathy toxic Any PT under MedDRA Nephropathies HLGT	Allergic bronchitis Acute interstitial pneumonitis Asthma Allergic granulomatous angiitis Alveolitis Alveolitis allergic Angiolympoid hyperplasia with Eosinophilia Eosinophilic bronchitis Eosinophilia myalgia syndrome Eosinophilic pneumonia Interstitial lung disease Pleural effusion Pleurisy Pleurisy viral Pleuropericarditis Pneumonitis Pulmonary eosinophilia Pulmonary vasculitis Pulmonary toxicity	Arteritis (any PT that includes the word "arteritis") Capillaritis Vasculitis (any PT that includes the word "vasculitis")

Appendix 13.3 Enlarged lymph nodes of at least 2 sites

Search for PT including the word “Lymphadenopathy” alone or as part of another PT

Such as some examples are given below:

- Lymphadenopathy Mediastinal
- Paratracheal Generalized
- Retroperitoneal
- Vaccination site

Search for other PT that could reflect lymphadenopathy

- Benign lymph node neoplasm
- Lymph node palpable
- Lymph node scan abnormal

